- 2- The lack of knowledge and information in the published studies about the effect of resisted exercise on improving insulin resistance post-burn.
- 3- This study will be carried out to investigate the effectiveness of resisted exercise in improving insulin resistance in post-burned patients.

The hyper metabolic response to injury is characterized by increased blood pressure and heart rate, peripheral insulin resistance, and increased protein and lipid catabolism, which lead to increased resting energy expenditure, increased body temperature, total body protein loss, muscle wasting, and stimulated synthesis of acute-phase proteins. These responses occur in all trauma, surgical, or critically ill patients, but the magnitude with which they occur and their duration are particularly severe and sustained for burn patients (**Gerd G Gauglitz et al, 2022**).

Delimitation

This study will be delimited in the following aspects:

Subjects

Sixty eight patients with insulin resistance post burn will participate in this study, they will be selected from government hospitals (general and insurance).

Will be randomly divided into two equal groups (group A, group B).

Their ages range from 18-35 years.

Equipment and tools:

Measurement:

Insulin resistance homeostasis model assessment [HOMA IR test].

Null hypothesis

There will be no effect for resisted exercise on insulin resistance post burn.

Basic assumption

It will be assumed that:

- All patients will be evaluated in the same way.
- All patients will be cooperative and follow instructions during the assessment procedures.
- The results obtained from this study will be of value in the physical therapy field.

Definition of terms:

The following terms will be defined and explained for a clear understanding of the terminology used in this study:

Insulin resistance

Insulin resistance is defined as the decreased tissue response to insulin-mediated cellular actions and is the inverse of insulin sensitivity. The term “insulin resistance,” as generally applied, refers to whole-body reduced glucose uptake in response to physiological insulin levels and its consequent effects on glucose and insulin metabolism. Euglycemic hyperinsulinemic clamp studies have shown that insulin resistance is determined primarily by the response of skeletal muscle, with over 75% of infused glucose taken up by muscle and only 2–3% by adipose tissue (**Claire**

Levy-Marchal et al, 2010).

Chapter II

Literature review

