and cardiovascular complications that accompany a severe burn can persist for up to three years post injury. Accordingly, there is now a greater appreciation of the need for strategies that can hasten recovery and reduce long-term morbidity post burn. RET (including resistance exercise and aerobic exercise) is a vital maneuver to restore normal body metabolism and glucose sensitivity in burn survivors. Given that RET is a safe and efficacious treatment that restores function and reduces post burn morbidity, the purpose is that a long-term exercise prescription plan should be considered for all patients with severe burns (**Alen Palackic et al, 2021**).

Chapter III

Subject, Materials and Methods

In this part of the study, the materials and methods will be presented under the following headings: subjects, equipment, procedures of the study and the statistical procedures.

Sample size

Sample size calculations will be performed using G*Power statistical software (version 3.1.9.2, Franz Faul, University Kiel, Germany) and will be revealed that the appropriate sample size for this study is N=68 patients, will be divided into two groups each consist of 34 patients, using the following assumptions: alpha level = 0.05, power = 0.90, effect size (Cohen's d) = 0.80, and two-tailed test.

Subjects

sixty-eight patients, who have upper limb, upper chest and upper back burn. Their ages will be ranged from 18-35 year old. Only patients around (20% - 40%) of total body surface area (TBSA) burned. The participants will be selected from government hospitals (General and insurance hospitals) and randomly distributed into 2 equal groups (group A, group B).

Design of the study:

In this study, the patients will be randomly assigned into two equal groups (34 patients for each group).

1.1_(a) Group A: (Study group)

This group includes 34 patients who have insulin resistance and who will receive resistance exercise and routine medical treatment. The patients will receive 3 sessions per week for 12 weeks, time of the session is 30 minutes.

1.1(b) Group B: (Control group)

This group includes 34 patients who have insulin resistance and who will receive routine medical treatment.

1.2 Criteria for Patients selection.

The criteria for patients selection are classified into two various criteria:

1.2 (a) Inclusion criteria

- Patients ranged from 18-35 years of age.
- Patients has waist hip ratio around 0.8 in female and 0.95 in male.

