- Participants were asked to fast for nine hours prior to coming in for blood testing. To maximize the validity of the glucose and insulin results, before the blood sample, participants filled out a fasting survey that asked specific questions addressing the last time they had consumed food or liquids. Included in the questionnaire were questions specific to the ingestion of less commonly thought of foods such as breath mints, gum, tea, alcohol, or supplements to ensure that the participants were following the fasting protocol. Blood samples of 89-92 mL were collected (**McKayla J. Niemann et al, 2020**).

- HOMA-IR test was performed for both groups before the treatment program, after the 6 weeks of the treatment program and after 12 weeks of the treatment program to evaluate the progression of insulin resistance in both groups.

Scoring

The HOMA-IR is defined as $[\text{fasting glucose (mmol/L)} \times \text{fasting insulin (\mu mol/L)}]/22.5$ or $[\text{fasting glucose (mg/dL)} \times \text{fasting insulin (\mu mol/L)}]/405$.

The HOMA score of <1.9 was considered as indicator of “Insulin sensitivity”; 1.9 to 2.9 as indicator of “Low IR” and >2.9 as indicator of Significant IR (**Haamid Bashir et al, 2022**).

3.2 Therapeutic procedures:

Procedures for the exercise program:

- Resisted exercise will be done for patients with upper back, upper chest and upper limb burn.
- Resisted exercise will target muscle groups of lower limb.
- Resisted exercise will be done by using sand bags, elastic bands and resisted machines.

-Three-Repetition Maximum Test

The first and second sessions of actual training will be spent with patients being tested for a three repetition maximum to establish training loads that will be used

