during the training period. The exercises will be performed included leg press, leg extension and leg curl. After an instruction period on correct exercise technique the patient will perform a warm-up to become familiar with the movement. Next, the weight will be progressively increased to which the patient can successfully perform four repetitions with correct technique. If four repetitions will be performed with correct technique a one minutes rest will be given and the weight will be increased. This will be repeated until the patient can perform three repetitions, with the fourth repetition not volitionally possible with correct technique, and the test will be terminated. The amount of weight lifted from the successful lift will be recorded as the individuals three repetition maximum. From this information, the basic 3 sets of 8-12 repetitions RM's were established.

Resisted Exercise Training Program

Rehabilitative exercise training will be performed as previously described. All exercises will be performed using free weights, elastic bands and variable-resistance machines. Modifications to exercises will be made when appropriate depending on the patient injury characteristics. The load will be gradually increased from 50-60% of 3RM at the beginning of the program up to 80-85% of 3RM (repetitions maximum) at the end of the program. All exercise sessions will be preceded by a 5-minute warm-up at <50% VO₂peak. No strength training activities will be permitted outside the supervised training session; however, both groups will be encouraged to maintain normal daily activities (**Justin P. Hardee et al, 2014**).

4- Statistical procedures:

- In this study, the mean, the standard deviation and the standard error will be calculated for all the patients (2 groups of the study) after the detected time of the study.
- The mean and the standard deviation will be used as a primary source of connecting facts about each parameter to measure central tendency.
- Repeated measure ANOVA test will be used to compare variables within each group to detect the level of significance in each group.
- Unpaired t-test to compare the variable between groups to detect significance level between two groups (comparison).
- The statistical package for social science (SPSS) will be utilized for data analysis and the level of significance set at 0.05 levels.

Reference

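### Both HOMA-IR formulas give fasting insulin in micromol/L, a unit that fits neither their divisors nor the 1.9 and 2.9 cut-offs printed beneath them

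*Protocol*

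**What the plan says.** Section 3.1 of the protocol (Measurement Procedures, under Scoring) gives two versions of HOMA-IR. With glucose in mmol/L the product is divided by 22.5: "fasting insulin (\mu mol/L)}]/22.5". With glucose in mg/dL it is divided by 405: "fasting insulin (\mu mol/L)}]/405". Both state insulin in micromol/L. No other part of the protocol gives an insulin unit; the HOMA background in the literature review has none.

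The same Scoring text sets three bands. The lowest begins "The HOMA score of <1.9 was considered as indicator of" insulin sensitivity, 1.9 to 2.9 is low insulin resistance, and the top band is ">2.9 as indicator of Significant IR".

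HOMA-IR is the only measurement listed under Delimitation ("Insulin resistance homeostasis model assessment [HOMA IR test"). It is taken before treatment and at 6 and 12 weeks. The Design section describes the study group as "This group includes 34 patients who have insulin resistance and who will receive resistance exercise and routine medical treatment" and the control group as "This group includes 34 patients who have insulin resistance and who will receive routine medical treatment". Section 4 plans that "the mean, the standard deviation and the standard error will be calculated for all the patients", followed by a repeated-measures ANOVA within groups and an unpaired t-test between groups.

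**The concern.** A HOMA-IR score has meaning only if the units of glucose and insulin match the divisor. Here the insulin unit does not match the cut-offs in the same paragraph, and the gap is more than five orders of magnitude.

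This is the operative definition of the sole outcome, not background text. Applied literally, the descriptive statistics in section 4 would be on the wrong scale and would not be comparable with other HOMA-IR results without back-conversion. Every patient would also fall in the insulin-sensitive band, although the Design section describes both groups as insulin resistant.

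A molar unit also invites a more realistic mistake, which is to enter insulin in pmol/L unconverted. That would inflate scores about six- to sevenfold, and such values could pass unnoticed. Patients come from several government hospitals, and the protocol gives no correct insulin unit that would keep entries uniform.

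**Working it through.** **Inputs from the protocol:** divisors 22.5 (glucose in mmol/L) and 405 (glucose in mg/dL); insulin in micromol/L; cut-offs 1.9 and 2.9; N = 68, alpha 0.05 two-sided, power 0.90, d = 0.80.

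**Assumptions not in the protocol:** fasting glucose 4.5 to 5.5 mmol/L; 1 microU/mL of insulin = 6.0 to 7.2 pmol/L.

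**1. Are the two formulas consistent with each other?** 405 / 22.5 = 18, the mmol/L to mg/dL factor for glucose. They agree on glucose and so need one common insulin unit.

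**2. What insulin figure do the cut-offs imply?** Insulin = HOMA-IR × 22.5 / glucose.

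| Glucose (mmol/L) | Insulin figure at 1.9 | Insulin figure at 2.9 |
|---|---|---|
| 4.5 | 9.50 | 14.50 |
| 5.0 | 8.55 | 13.05 |
| 5.5 | 7.77 | 11.86 |

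In microU/mL these are plausible fasting values. In micromol/L, the figures for a score of 1.9 convert to:
- low end: 7.77 × 1,000,000 / 7.2 = about 1.08 million microU/mL
- high end: 9.50 × 1,000,000 / 6.0 = about 1.58 million microU/mL

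No patient can have such values.

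**3. What does a patient score?** Take glucose 5 mmol/L (90 mg/dL) and insulin 10 microU/mL.
- Insulin in microU/mL: 5 × 10 / 22.5 = 2.22, and 90 × 10 / 405 = 2.22. The two formulas agree, and the class is low insulin resistance.
- As written: 10 microU/mL is 0.000060 to 0.000072 micromol/L, so 5 × that / 22.5 = 0.0000133 to 0.0000160.
- Ratio: 1 / 0.0000072 = 138,889 to 1 / 0.0000060 = 166,667 times too small.

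**4. Could any patient reach 1.9 as written?** Take an assumed extreme of glucose 15 mmol/L and insulin 300 microU/mL. In microU/mL the score is 15 × 300 / 22.5 = 200. As written it is 200 × 0.0000060 to 200 × 0.0000072 = 0.0012 to 0.0014, still far below 1.9.

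**5. What if pmol/L values are entered unconverted?** For the patient in step 3, 5 × 60 / 22.5 = 13.3 and 5 × 72 / 22.5 = 16.0, instead of 2.22. A patient with glucose 5 mmol/L and insulin 4 microU/mL should score 5 × 4 / 22.5 = 0.89 (insulin sensitive). Entered as 24 to 28.8 pmol/L, the score is 5.3 to 6.4 (significant insulin resistance).

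**6. Are the tests affected?** Multiplying every score by a constant k multiplies the mean difference and its standard error by k, so t and Cohen's d are unchanged. In the ANOVA each mean square is multiplied by k², so F is unchanged. A check on simulated data with 34 per arm gave t = -2.587 and p = 0.0119 at k = 1, 6, 0.000006 and 0.000006945.

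**7. Sample size.** The two-sample t-test calculation gives 33.83 per arm, rounded up to 34, so N = 68 with power 0.9015. The protocol's figure is reproduced and does not depend on the insulin unit.

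**The case against.** The strongest reply is that this is a label, not a method. If the laboratory reports insulin in its usual unit and staff put that number into the formula, the scores will be right whatever the protocol prints. The factor of roughly 139,000 to 167,000 arises only if someone actually converts to micromol/L. A constant factor leaves every planned test unchanged, and a known factor can be reversed. The 1.9 and 2.9 bands appear in neither the eligibility list nor section 4, and the statement that patients have insulin resistance is not tied to a HOMA-IR value. The symbol may also have been misread when the PDF was converted. Both formulas stand on one line, so the repetition is not independent confirmation.

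Much of this stands. The effect on inference is nil if one unit is used throughout, and the symbol should be checked against the PDF. Mixed units between laboratories or visits would bias the group comparison, but the protocol does not say that mixing will occur.

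It does not remove the error. The unit is stated in the protocol itself, in the rule that defines the only outcome, and nothing elsewhere corrects it. The conversion factor and glucose range are assumptions, but no plausible choice closes a gap of this size.

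**Conclusion.** The insulin unit is wrong as written in both formulas and should be corrected. Followed literally, scores come out about 139,000 to 167,000 times too small, every patient is classed as insulin sensitive, and the planned means, SDs and SEs are wrong by the same factor. The size rests on the assumed 6.0 to 7.2 pmol/L per microU/mL; the conclusion does not depend on the exact value. P-values, the standardised effect and N = 68 are unaffected provided one unit is used throughout. It is most likely a labelling slip, subject to a look at the PDF.

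**What to change.** In the Scoring text of section 3.1, give fasting insulin in microU/mL (equivalently mU/L) in both formulas: glucose (mmol/L) × insulin (microU/mL) / 22.5, or glucose (mg/dL) × insulin (microU/mL) / 405. State that every hospital laboratory reports insulin in that unit at all three visits, or that results are converted by one stated factor before HOMA-IR is calculated. Add a unit field to the data form.

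The cost is a one-line correction and one form field. The sample size and the planned tests stay as they are.

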Though the development of type 2 diabetes is the most obvious and direct consequence of insulin resistance and β (beta)-cell stress that proceeds unchecked, there are myriad other associations that healthcare providers should be aware of and screen for as indicated. Like insulin resistance, many of these conditions are more commonly seen in adulthood, but can certainly affect the pediatric population. Many of these disease associations and syndromes are not entirely surprising, given the multi organ effects of insulin even beyond glucose homeostatic mechanisms. Resistance to insulin-mediated control of circulating fatty acids may predispose to worsening dyslipidemia, a well-known risk factor for cardiovascular disease. Insulin, in addition, increases androgen synthesis and simultaneously decreases liver production of sex hormone-binding globulin, thus providing a mechanism for the reproductive disruption seen in PCOS. Consequently, insulin resistance itself is

associated with many well-known diseases and syndromes that incorporate other organ and system effects of insulin (**Melinda E. Chen et al, 2019**).

Model assessments of insulin resistance:

Homeostasis Assessment Model (HOMA). The Homeostasis Assessment Model is a mathematical model which allows values for insulin sensitivity and β -cell function (expressed as a percentage of normal) to be obtained if simultaneous fasting plasma glucose and fasting insulin/C-peptide concentrations are known. Since insulin secretion is pulsatile, the optimal sample should be the mean of three results at 5-min intervals (0, 5, and 10-min samples). However, many researchers have used single basal samples for epidemiological studies. HOMA modelling is an appropriate method for assessing change in insulin resistance with time in individuals.

HOMA has proved be a robust method for assessing insulin resistance in groups of patients over long periods of time because the sampling is simple, and the result is available without complex computing as soon as fasting glucose and insulin values are available.

Estimates of insulin resistance from HOMA correlate well with estimates from the euglycaemic clamp ($Rs = 0.88$, $P < 0.0001$, $Rs = 0.85$, $P < 0.0001$). Although the coefficient of variation (CV) for HOMA was initially reported as 31%.

A potential source of confusion is that of terminology, which has sometimes allocated normal insulin resistance as 1 or 100%. Sensitivity has always been

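### The between-group test ignores the baseline HOMA-IR already collected, and no section says whether week 6 or week 12 decides the null hypothesis

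*Protocol*

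**What the plan says.** **Hypothesis.** The protocol's null hypothesis is "There will be no effect for resisted exercise on insulin resistance post burn". It names no visit.

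**Measurements.** Chapter III, section 3.1 schedules HOMA-IR before the programme and at 6 and 12 weeks after its start. The two later visits are listed on an equal footing. For the study group, "The patients will receive 3 sessions per week for 12 weeks", so week 12 is the end of treatment.

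**Sample size.** The calculation uses "alpha level = 0.05, power = 0.90, effect size" (Cohen's d) of 0.80 and a two-tailed test, giving 68 patients, 34 per group. No visit is attached to the effect size.

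**Analysis.** Section 4 (Statistical procedures) gives the between-group analysis in one bullet: "Unpaired t-test to compare the variable between groups to detect significance level between two groups (comparison". A separate bullet covers change within arms: "Repeated measure ANOVA test will be used to compare variables within each group to detect the level of significance in each group". A common threshold follows: "the level of significance set at 0.05 levels". The only time reference in section 4 is "after the detected time of the study". It belongs to the bullet on means, standard deviations and standard errors, not to the t-test, and it identifies no visit.

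**The concern.** There are two gaps in one bullet.

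First, the stated test uses only the values at the tested visit. Every patient also contributes a baseline HOMA-IR. If that baseline correlates with the later value, as repeated measurements of one quantity in the same patient usually do, an unadjusted comparison leaves explainable variation in the error term. It also leaves chance baseline differences between two arms of 34 uncorrected.

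Second, the bullet refers to the variable without a visit, while two post-baseline visits exist. The stated 0.05 and 0.90 apply to one test at one visit where d = 0.80 holds. If the deciding visit could be settled after both results were known, the false-positive rate would no longer be 5%.

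**Working it through.** **Inputs from the protocol:** 34 per arm, two-sided alpha 0.05, d = 0.80, target power 0.90.

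**Assumed, because the protocol does not give it:** the correlation ρ between HOMA-IR values at different visits. I use 0.3 to 0.7 for power and 0.3 to 0.9 for the error rate, with equal SDs at all visits.

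**1. Reproducing the sample size.** For an unpaired t-test with n per arm, the noncentrality is d × √(n/2) with 2n − 2 degrees of freedom.
- n = 34: 0.80 × √17 = 3.298; critical t on 66 df = 1.997; power = 0.9015.
- n = 33: power = 0.893, below the target.

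So 34 per arm, 68 in total, is confirmed.

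**2. Error rate if either visit's value could decide.** With two independent tests the rate would be 1 − 0.95² = 0.0975. The two tests share patients, so the true figure is lower. Simulation with no treatment effect, 34 per arm and 200,000 trials per correlation (Monte Carlo standard error below 0.001) gives:

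| ρ | Week 12 only | Week 6 or week 12 |
|---|---|---|
| 0.3 | 0.050 | 0.095 |
| 0.5 | 0.050 | 0.090 to 0.091 |
| 0.7 | 0.050 | 0.083 to 0.084 |
| 0.9 | 0.050 | 0.071 |

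Two values in a cell come from two separate runs. The range is therefore about 7% to 9.5%.

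**3. Power of the week-12 comparison, unadjusted and adjusted.** Adjusting for baseline multiplies the residual SD by √(1 − ρ²). A 0.8 SD effect on the week-12 value becomes an effective d of 0.8/√(1 − ρ²), tested on 65 df.

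| ρ | Effective d | Noncentrality (d × √17) | Power, ANCOVA | Power, unadjusted t-test |
|---|---|---|---|---|
| 0.3 | 0.839 | 3.458 | 0.926 | 0.9015 |
| 0.5 | 0.924 | 3.809 | 0.963 | 0.9015 |
| 0.7 | 1.120 | 4.619 | 0.995 | 0.9015 |

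The formula ignores the small loss from chance baseline imbalance. Simulation that includes the imbalance gives 0.923, 0.961 and 0.995. The false-positive rate of the adjusted test stays at 0.050 to 0.051.

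If baseline were useless (ρ = 0), the formula gives power 0.9014, so giving up one degree of freedom costs practically nothing.

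**The case against.** The strongest reply is that nothing is misstated. The unpaired t-test is a valid randomised comparison. The sample size is built for exactly one such comparison, and a 12-week programme points to week 12. On that reading the error rate is 5% and the power 0.90. A separate statistical analysis plan, if one exists, may also settle details. Most of this stands, and it is why the point is about improving and completing the plan rather than about an error in it. What remains is that the deciding visit for the only outcome belongs with the endpoint in the protocol, and that section 4 itself fixes a test which ignores the baseline.

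Three stronger readings are tempting and are not supported:

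- **That the trial will test both visits and claim success on either.** The protocol does not say so. The 7% to 9.5% describes what the wording leaves open, not a declared rule.
- **That choosing between the value and the change from baseline inflates the error further.** The protocol defines no change score for the t-test. The plain reading of the bullet is the measured HOMA-IR.
- **That the within-group ANOVAs are meant to prove an exercise effect.** Section 4 keeps the within-group and between-group bullets apart and makes no such claim. An arm compared with itself cannot test exercise against control, so calling these analyses supportive is useful, but no misuse is planned.

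**Conclusion.** The concern holds in a limited form. Section 4 specifies a less efficient between-group test than the collected data allow, and the protocol does not name the deciding visit. A reader should not infer that N = 68 or the t-test is wrong; both are sound for a single two-sided comparison.

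The gain from adjustment is power of about 0.93, 0.96 and above 0.99 instead of 0.90, at correlations of 0.3, 0.5 and 0.7. The exposure from the unnamed visit is a false-positive rate of about 7% to 9.5%, and only if either visit were allowed to decide. Both results rest on the assumed correlations and equal SDs. The power figures also require d = 0.80 to refer to the week-12 value, which the protocol does not state. This should be fixed before results are seen.

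**What to change.** Replace the between-group bullet in section 4 with:

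*The single confirmatory test is the between-group comparison of HOMA-IR at week 12 by ANCOVA adjusted for baseline HOMA-IR, two-sided 0.05; week 6 and the within-group analyses are supportive.*

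Add to the sample size paragraph that d = 0.80 refers to the week-12 value.

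**Cost.** One bullet and one clause. There are no extra patients, visits or blood samples: baseline HOMA-IR is already scheduled, SPSS runs ANCOVA, and N = 68 stands. The downside is that an effect seen only at week 6 could not be claimed as confirmatory. Keeping both visits confirmatory would be dearer. Splitting alpha to 0.025 each lowers the power of each unadjusted test to 0.84 at 34 per arm, and about 41 per arm (82 in total) would be needed to restore 0.90.

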- Patient has body mass index (BMI around 25 kg/m²) (**J Obes Weight Loss Ther, 2015**).
- Patients has second degree thermal burn injury (superficial and deep partial thickness).
- Patients with around (20% - 40%) of total body surface area (TBSA) burned.
- Patients who are able to follow verbal commands.
- Patients will have upper limb, upper chest and upper back burn.
- Patients with normal hemoglobin A1C (5.6 %).
- Patients should take diet rich protein, omega 3 and should have good sleep.
- Patients passed two months post severe burns (**Melanie G. Cree et al, 2008**).

1.2 (b) Exclusion criteria

- Potential participants were excluded if they reported a leg amputation, anoxic brain injury, psychological disorders, quadriplegia, or severe behavior or cognitive disorders history of heart disease, stroke, diabetes mellitus, or any condition that would prevent them from engaging in an exercise study.
- Patients with liver disease, pancreatic disease or any disease affects metabolism.
- If they were already engaging in 2 or more planned exercise sessions per week.
- Patients with any medication to lower glucose levels. Blood pressure and medications to lower lipid levels (**Lance E. Davidson et al, 2009**).

2. Equipment and Tools:

Equipment in this study will be divided into two main categories; therapeutic and measuring equipment.

2.1. Therapeutic Equipment:

Resisted exercise program will be done by using:

- 1- Sand bags.

- 2-Elastic bands.

3- Resistance machines.

2.2. Measuring Equipment:

The following tools are used to assess the insulin resistance:

-HOMA-IR analysis will be used to assess insulin resistance by taking

Blood sample using sterile syringe 5 cm (**Pilar Gayoso-Diz et al, 2013**).

3. Procedures of the study:

The procedures of this study are classified into the following:

3.1 Measurement Procedures:

In this phase HOMA-IR analysis measurements:

All measurements will be taken before the treatment program, 6 weeks after the beginning of treatment program and 12 weeks after the beginning of the treatment program.

Assessment of insulin resistance:

- By doing HOMA-IR analysis.

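### The only between-group test is an unadjusted t-test; it is valid, but adjusting for the baseline HOMA-IR already collected would be more precise

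*Protocol*

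**What the plan says.** The protocol's section 4 (Statistical procedures) names two inferential methods. The first works inside each group: "Repeated measure ANOVA test will be used to compare variables within each group to detect the level of significance in each group". The second is the only comparison of the groups with each other: "Unpaired t-test to compare the variable between groups to detect significance level between two groups (comparison". No covariate, change score, group-by-time term or time point is given for it.

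The outcome is measured three times. Section 3.1 states: "All measurements will be taken before the treatment program, 6 weeks after the beginning of treatment program and 12 weeks after". The text on assessment of insulin resistance confirms that this applies to both arms: "HOMA-IR test was performed for both groups before the treatment program, after the 6 weeks of the treatment program".

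The Sample size section gives the assumptions "alpha level = 0.05, power = 0.90, effect size (Cohen's d) = 0.80, and two-tailed test" and concludes that "the appropriate sample size for this study is N=68 patients, will be divided into two groups each consist of 34 patients".

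**The concern.** The trial asks whether resisted exercise changes insulin resistance. Of the two named methods, only the comparison between randomised groups answers that, so the unpaired t-test carries the trial's conclusion. As written, it does not use the baseline HOMA-IR that every patient provides.

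If baseline predicts the week-12 value, leaving it out means a larger standard error than necessary. It also leaves any chance difference between the groups at baseline in the estimate. These are two views of the same loss, not two separate faults.

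The loss matters more here because 68 is the smallest total that reaches 90% power with the planned test, so there is no spare precision.

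It is also unclear what the tested variable is. It could be the week-6 value, the week-12 value or a change from baseline. A change score would use baseline, but less efficiently than ANCOVA.

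**Working it through.** **Inputs from the protocol.** Two-sided alpha 0.05, power 0.90, d = 0.80, n = 34 per group (Sample size); unpaired t-test (section 4).

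**Assumed input.** The correlation rho between baseline and week-12 HOMA-IR is not in the protocol. I take 0.2 to 0.7, and also show lower values.

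**Step 1: reproduce the planned sample size.** The noncentrality is d × sqrt(n/2), with 2n − 2 degrees of freedom.
- n = 34: 0.80 × sqrt(17) = 3.298, df 66, power 0.9015.
- n = 33: power 0.8926.

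The stated 34 per group is therefore exactly what an unadjusted two-sample t-test needs.

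**Step 2: ANCOVA with baseline as covariate.** The variance of the group difference is multiplied by (1 − rho²). Estimating the slope inflates it by about 1 + 1/(2n − 4) = 1 + 1/64 at n = 34. The noncentrality becomes 3.298 / sqrt[(1 − rho²) × 65/64], with 2n − 3 = 65 degrees of freedom. At rho = 0.5 this is 3.298 / sqrt(0.75 × 1.0156) = 3.779, giving power 0.961.

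| rho | Power, ANCOVA, 34 per group | Effect detectable at 90% power (SD) | Patients per group for 90% power |
|---|---|---|---|
| 0 | 0.897 | 0.804 | 35 |
| 0.1 | 0.900 | 0.800 | 35 |
| 0.2 | 0.908 | 0.788 | 34 |
| 0.3 | 0.922 | 0.767 | 32 |
| 0.5 | 0.961 | 0.697 | 27 |
| 0.7 | 0.995 | 0.574 | 19 |
| t-test | 0.9015 | 0.798 | 34 |

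At rho = 0.1 the power is 0.8998, just under the target. ANCOVA and the t-test have equal power at rho of about 0.126. Simulation of 20,000 normal trials at each of rho 0.2, 0.3, 0.5 and 0.7 gave ANCOVA powers of 0.908, 0.921, 0.963 and 0.995, in agreement with the table.

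**Step 3: the change-score reading.** Suppose d = 0.80 is in units of the week-12 SD and the SDs are equal at both times. The change score then has SD factor sqrt[2(1 − rho)], and power with 34 per group is 0.729, 0.784, 0.902 and 0.987 at rho 0.2, 0.3, 0.5 and 0.7. Each is below the ANCOVA figure. Under this reading the planned 90% is missed when rho is below about 0.5.

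**Step 4: chance imbalance.** The standardised baseline difference has SD sqrt(2/34) = 0.2425. A difference above 0.3 SD in either direction has probability 0.22. Such a difference shifts the unadjusted estimate by rho × 0.3, that is 0.06 SD at rho 0.2 and 0.21 SD at rho 0.7. The t-test's confidence interval already allows for this across repeated trials; ANCOVA removes the predictable part in the trial at hand.

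**The case against.** The strongest reply is that nothing here is wrong. The t-test is valid under randomisation, the sample size was calculated for that test, and the two agree. On this view ANCOVA is a preference between two sound methods. That the test is valid stands, and no bias is alleged. But the protocol itself fixes the test that answers its question and leaves out information it already collects, so this is more than a detail that can be left to an analysis plan.

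The second reply is that the size of the gain depends on a correlation the protocol does not give. This also stands. The narrow eligibility criteria, and the 31% coefficient of variation that the literature review says was initially reported for HOMA, may put rho at the low end. There the gain is about 1 to 2 percentage points of power and 0 to 2 patients per group. Below about 0.13 there is a slight loss. The balance still favours adjustment: at worst about half a point of power is lost, against a gain of about 6 points at rho 0.5 and 9 at rho 0.7.

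Third, the change-score shortfall depends on scale. If d = 0.80 was meant in units of the SD of change, the planned test has 90% power by construction. The protocol does not say which was meant, so the shortfall is conditional.

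Finally, an ANCOVA of week 12 also selects a time point, which the protocol does not do. That is a separate choice and should be made openly.

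**Conclusion.** The point holds as a matter of efficiency, not validity. The sole between-group comparison is unadjusted and makes no stated use of baseline HOMA-IR. With 34 per group and d = 0.80, adjustment would raise power from 0.90 to 0.91 at rho 0.2, 0.92 at 0.3, 0.96 at 0.5 and 0.995 at 0.7. Equivalently, the effect detectable at 90% power would fall from 0.80 SD to 0.79, 0.77, 0.70 or 0.57 SD.

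These figures assume normally distributed values, a common within-group correlation, d expressed in week-12 SD, and all 68 patients analysed. Because rho is unknown, the benefit could be very small. The change should be made, but the trial does not fail without it.

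**What to change.** In section 4, replace the between-group t-test with an ANCOVA of week-12 HOMA-IR, with group as factor and baseline HOMA-IR as covariate. Report the adjusted mean difference with its 95% confidence interval. Keep the unpaired t-test as a sensitivity analysis and state which value it compares. State also that week 12 is the time point of the main comparison, and how any week-6 group comparison is to be treated.

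Make the change before outcome data are seen, because adjustment chosen afterwards would be open to challenge. The cost is a few lines of wording and one degree of freedom, plus about half a point of power if baseline turns out to be unrelated to outcome. It needs no new data or visits, and the total of 68 is unchanged.
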